5.4.2 Randomized Portion

5.4.2.1 All patients will be provided with a medication/blood glucose log, a blood glucose monitor, and taught to perform self fingerstick glucose draws (see Appendices II-VI). The first blood glucose draw will be done by a nurse or research team member on the visit 5-9 days prior to SRS and the initial value will be recorded in the blood glucose log.

5.4.2.2 If the Pilot Portion (at either full dose or at one dose reduction) demonstrates no "**serious toxicities**" and ≤ 3 "**concerning toxicities**" (described in section 5.3.1), patients in the Randomized Portion of the trial will be taught and instructed to measure blood glucose levels once a day (in the morning before breakfast (fasting)) starting at the initiation of the investigational medication and continuing for at least the first week after SRS. If no "**concerning toxicities**" or "**serious toxicities**" are found at the one week post SRS visit, then the patient may proceed through the rest of the trial with no further need to assess blood glucose via the fingerstick draws. If the patient does experience a "**concerning toxicity**" or "**serious toxicity**" then he/she must discontinue their investigational medication (as per section 5.3.2) and will not have to continue checking their blood glucose levels.

5.4.2.3 If the Pilot Portion (at either full dose or at one dose reduction) demonstrates no "**serious toxicities**" and 4-5 "**concerning toxicities**" (described in section 5.3.1), patients in the Randomized Portion of the trial will be taught and instructed to measure blood glucose as per section 5.4.1.

5.5 Radiation Therapy

The radiation dose range is 18-24 Gy in a single fraction or 25-30Gy in 5 fractions for patients with a total tumor volume $\leq 10 \text{ cm}^3$ and 15-22 Gy in a single fraction for 25-30Gy in 5 fractions for a total tumor volume $> 10 \text{ cm}^3$ (14).

For brain stem lesions treated in a single fraction, the following dosing may be followed:

- Tumor volume of $0-1 \text{ cm}^3$ = dose range of 18-20 Gy
- Tumor volume of $> 1 - 4 \text{ cm}^3$ = dose range of 16-18 Gy
- Tumor volume of $> 4 \text{ cm}^3$ = dose range of 14-15 Gy

5.6 Treatment Calendar

Please see Appendix VIII: Study Schedule of Events for further details.

6.0 RADIATION THERAPY

6.1 Timing of Radiation Therapy

Stereotactic radiosurgery (SRS) should be delivered at least 5 days after initiating the glyburide (Pilot Portion) or investigational medication (Randomized Portion).

It is possible at the time of SRS/MRI for treatment planning that one of these scenarios occurs in which the patient should be removed from the protocol (thus making the patient inevaluable):

1. An identified metastasis at the time of registration now exceeds the acceptable upper limit diameter are visualized. Any such lesion should not be treated with SRS and the patient should be removed from the protocol.
2. If the lesions are not visualized, radiosurgery should not be delivered and the patient should be removed from the protocol.
3. If patient is unable to proceed with SRS for any reason (such as claustrophobia, location of lesion and head anatomy make treatment physically impossible, etc.), SRS should not be delivered and the patient should be removed from the protocol.

6.2 Technical Factors

Treatment shall be delivered with linac-based radiosurgery machines. A treatment planning system capable of generating isodose distributions in three dimensions for a given treatment is required.

6.3 Localization, Simulation, and Immobilization

All institutions must use FDA-approved stereotactic localization procedures for imaging and treatment delivery. MRI may be performed within 21 days prior to SRS treatment and can be fused with CT done at the time of simulation [treatment planning] for linac-based radiosurgery per standard institutional guidelines. Intravenous gadolinium administration is required for the MRI.

Stereotactic MRI slice thickness may not exceed 5 mm.

6.4 Treatment Planning

6.4.1 Total Dose Determination

The total dose should be 18-24 Gy for tumors < 2cm in diameter and 15-22 Gy for tumors > 2cm in diameter.

Alternatively, a 5 fraction radiosurgery plan using 25Gy in 5 fractions or 30Gy in 5 fractions may be utilized.

6.4.2 Dose Prescription

The minimum dose shall be established by the SRS treatment planning software or by an examination of the dose distribution on each axial level on which the target volume has been defined, and/or by the target dose-volume histogram.

6.4.3 Dose Limitation to Critical Structures

Single fraction plans: The maximum dose to the Optic Nerve and Chiasm should not exceed 10Gy (point dose up to 12 gy is allowed). The brainstem max is generally kept to a max of 12.5Gy. This volume may be allowed to exceed this to up to 16 Gy to a point dose. All radiosurgery plans will be peer reviewed for safety.

Five fraction plans: The maximum dose to the Optic Nerve and Chiasm should not exceed 25Gy (point dose up to 30 gy is allowed). The brainstem max is generally kept to a max of 31Gy. This volume may be allowed to exceed this to up to 35 Gy to a point dose. All radiosurgery plans will be peer reviewed for safety.

6.4.4 Target Volume

The target volume will include the enhancing portion of the metastatic lesions. Surrounding areas of edema will not be considered part of the target volume.

6.5 Radiosurgery Treatment Planning Data

6.5.1 Isodose distributions must be calculated, and the prescription isodose line clearly designated, for each target lesion in the transverse, coronal, and sagittal planes.

6.5.2 The isodose distributions on the required three planes for each target lesion will include isodose lines (in % dose) that represent 10% dose increments.

6.6 Treatment Planning Goals

6.6.1 Target Coverage QA

6.6.1.1 *Per protocol:* The submitted 90% isodose line (90% of the prescription dose, not total dose) completely encompasses target.

6.6.1.2 *Acceptable variation:* 80% isodose line covers the target.

6.6.1.3 *Unacceptable deviation:* 80% isodose line does not cover target.

6.6.2 Dose Homogeneity QA

The ratio of the maximum dose to the prescribed dose (MD/PD) is:

6.6.2.1 *Per protocol* if ≤ 2 .

6.6.2.2 *Acceptable variation* if > 2 but ≤ 2.5 .

6.6.2.3 *Unacceptable deviation* if > 2.5 .

7.0 DRUG THERAPY

7.1 Pilot Portion

7.1.1 Non-Micronized glyburide (1.25 mg po BID) should be administered orally twice a day beginning at least 5 days prior to SRS. Glyburide will be taken in the morning with breakfast and in the evening with dinner. All patients on the Pilot Portion of the study will receive glyburide which will continue until the evening dose on the day of one month post SRS follow-up MRI. If the patient misses a dose at any time, it will not be made up. All doses (whether missed or taken) should be recorded in the medication administration log.

7.1.2 In the event of a DLT between the time of glyburide initiation and the time of the one month follow-up MRI at full dose glyburide, one dose reduction will take place (the dose reduction will be immediate if there is one patient with a “*serious toxicity*”, but a full analysis may be required to determine if there are 6 or more patients with “*concerning toxicities*” which would warrant a dose reduction). The patient who experienced the DLT will stop glyburide

immediately. If the DLT was a “*concerning toxicity*”, all other patients currently on treatment at the time may continue at their current full dose glyburide. If the DLT was a “*serious toxicity*”, all other patients currently on treatment will be dose reduced immediately.

7.1.2.1 For patients who have already begun glyburide and require an immediate dose reduction, the full dose glyburide tablets will be returned to the study team and in turn to the UAB Investigational Drug Services (IDS) pharmacy. Subsequently 0.75 mg non-micronized glyburide will be dispensed to the patient and administered orally twice a day (in the morning with breakfast and in the evening with dinner) until the evening dose on the day of one month follow-up MRI.

7.1.3 In the event of a DLT on the reduced dose of glyburide, the trial will be terminated. The termination could be immediate if there is one patient with a “*serious toxicity*”, but a full analysis may be required to determine if there are 6 or more patients with “*concerning toxicities*” which would warrant study termination. The patient who experienced the DLT will stop glyburide immediately. If the DLT is a “*concerning toxicity*”, all other patients currently on treatment at the time may continue at their current dose reduced glyburide. If the DLT is a “*serious toxicity*”, all other patients currently on treatment will stop glyburide immediately.

7.1.4 If a patient suffers a DLT (either a “*concerning toxicity*” or a “*serious toxicity*”) after registration but before SRS, he/she will be removed from the protocol and considered inevaluable.

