2.3 Primary Endpoints

2.3.1 Pilot Portion: Occurrence of Dose Limiting Toxicities (DLTs) between the time of glyburide initiation and the time of the one month follow-up MRI.

2.3.2 Randomized Portion: Occurrence of edema increase and initiation of dexamethasone (or any corticosteroid administration with the purpose of treating cerebral edema) between the time of SRS* and the time of the one month follow-up MRI.

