Appendix VII for Adverse Event (AE) definitions and grading scale information.

If multiple toxicities are seen, the presence of a DLT should be based on the most severe toxicity experienced. Any patient who achieves a DLT will be taken off of glyburide immediately, but will still be evaluable.

Concerning Toxicity

1. Any **asymptomatic grade 3 or 4 hypoglycemia** as defined by CTCAE version 4.0.
2. Any **non-hematologic grade 3 or greater toxicity** (including neurologic toxicity) that is associated with a blood glucose level ≤ 80 mg/dl and is resolved with “low blood sugar intervention” (e.g. a return of blood glucose level to ≥ 80 mg/dl). **See Section 5.4.1.1 for a List of Low Blood Sugar Interventions.**

Serious Toxicity

1. Any **grade 5 toxicity** that is deemed by the investigator to be **at least possibly attributable to glyburide**.
2. Any **symptomatic grade 3 or 4 hypoglycemia associated with a non-hematologic grade 3 or greater toxicity** that is not resolved with “low blood sugar intervention” (e.g. does not

return to blood glucose level to ≥ 80 mg/dl) that is deemed by the investigator to be at least possibly attributable to glyburide. **See Section 5.4.1.1 for a List of Low Blood Sugar Interventions.**

Glyburide will be discontinued for any patient that meets the criteria for either a "**concerning toxicity**" or "**serious toxicity**". These patients will still be evaluable.

Any "**concerning toxicity**" that is observed in at least 6 (of 10 evaluable) patients will trigger a dose reduction (see section 7.1). After 1 dose reduction, if at least 6 (of 10 evaluable) patients are observed to have a "**concerning toxicity**", the study will be terminated.

Any "**serious toxicity**" that is observed in at least 1 (of 10 evaluable) patients will trigger a dose reduction. After 1 dose reduction, if at least 1 (of 10 evaluable) patients is observed to have a "**serious toxicity**", the study will be terminated.

5.3.1.1 If a dose reduction should occur, it will occur once the pre-specified DLT is reached.

Glyburide will be reduced to 0.75 mg po BID. In the event this dose reduction should occur, the Pilot Portion will be performed using the reduced dose (e.g. 10 evaluable patients are required to be assessed). If another DLT is observed at the reduced glyburide dose warranting a dose reduction, the study will be terminated.

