5.3.1.2 The patient who experiences a DLT (e.g. either a "**concerning toxicity**" or "**serious toxicity**") will stop glyburide immediately, but will still be evaluable. If the DLT is a "**concerning toxicity**", all other patients currently on treatment at the time may continue at their current glyburide dose. If the DLT is a "**serious toxicity**", all other patients currently on treatment will either be dose reduced immediately (if on full dose glyburide) or stop glyburide immediately (if on reduced dose glyburide). All other patients will still be evaluable.

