9.3 Analytic plan for primary objective

9.3.1 Pilot Portion: Each evaluable patient will be assessed for “*concerning toxicities*” and “*serious toxicities*”. If 6 or more patients demonstrate a “*concerning toxicity*” or 1 or more patients experience a “*serious toxicity*”, the therapy will be considered not feasible to deliver and one dose reduction will occur. If 6 or more patients demonstrate a “*concerning toxicity*” or 1 or more patients experience a “*serious toxicity*” on the dose reduced schedule, the intervention will be considered too toxic and the protocol will be terminated. Inevaluable patients will be replaced.

9.3.2 Randomized Portion:

After the acceptable glyburide dose has been established, the randomized portion will commence. No formal interim monitoring will take place and study analysis will be done when all 20 randomized patients are accrued in each treatment regimen. The results from this portion of the trial will be used as a screening mechanism for assessing whether glyburide should be studied in a formal randomized trial. The number of patients who experience treatment successes will be compared between the two regimens using the

exact test of proportions. If this test yields a one-sided test of equality of proportions of treatment success obtains a p-value of 0.30 or less, glyburide treatment will be considered as sufficiently interesting for further study. Otherwise, glyburide will be considered not interesting for further development. We acknowledge that the type 1 error rate of 0.30 is liberal, and note that this was chosen based on the preliminary efficacy aspect of the study; post-analysis power calculations may be performed.

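### Pilot section 7.1.4 makes patients with a DLT before SRS inevaluable, which contradicts the DLT window and can drop early toxicities from the dose-reduction and termination rule

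*Combined protocol and SAP*

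**What the plan says.** The pilot primary endpoint in 2.3.1, repeated in 9.1.1, is "Occurrence of Dose Limiting Toxicities (DLTs) between the time of glyburide initiation and the time of the one month follow-up MRI". Section 7.1.1 starts glyburide at least 5 days before SRS, so the window includes days before radiosurgery.

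Section 5.3.1 says: "Any patient who achieves a DLT will be taken off of glyburide immediately, but will still be evaluable". Section 7.3.4 repeats this for the pilot, and 5.3.1.2 says that the patient "will stop glyburide immediately, but will still be evaluable". None of the three makes an exception for timing.

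The thresholds in 5.3.1 are on evaluable patients. A concerning toxicity "that is observed in at least 6 (of 10 evaluable) patients will trigger a dose reduction"; for a serious toxicity the threshold is 1 of 10 evaluable. After one dose reduction, the same counts terminate the study. Section 9.3.1 likewise assesses each evaluable patient.

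Section 7.1.2 opens "In the event of a DLT between the time of glyburide initiation and the time of the one month follow-up MRI" and makes the reduction immediate for one serious toxicity. For concerning toxicities, "a full analysis may be required to determine if there are 6 or more patients with" that toxicity. It does not restrict either trigger to evaluable patients.

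Section 7.1.4 then says that a patient with either type of DLT "after registration but before SRS, he/she will be removed from the protocol and considered inevaluable". Sections 5.1 and 9.3.1 add: "Inevaluable patients will be replaced".

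**The concern.** The same patient is evaluable under three sections and inevaluable under a fourth, and the status decides whether the event enters the pilot's formal rule. That rule sends the dose forward, reduces it or ends the study.

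The days before SRS are part of the safety period. Patients are on drug, and 4.1.4.4 has them check glucose four times a day from the first dose. A serious toxicity under 5.3.1 includes a death at least possibly attributable to glyburide. If it fell before SRS, 7.1.2 would require an immediate dose reduction, while a literal 7.1.4, read with the counts in 5.3.1, would replace the patient and leave the count at zero. Two careful readers could reach different decisions from the same data, and the error under 7.1.4 runs only one way, toward declaring the dose safe.

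**Working it through.** **The text, side by side**

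| Section | Pilot patient with a DLT before SRS |
|---|---|
| 2.3.1, 9.1.1 | Inside the endpoint window |
| 7.1.2 | Inside the trigger window; no restriction to evaluable patients |
| 5.3.1, 5.3.1.2, 7.3.4 | Stops glyburide, stays evaluable |
| 4.1.9 | Stops glyburide; only corticosteroid use before SRS is marked inevaluable |
| 7.1.4 | Removed, inevaluable |
| 5.1, 9.3.1 | If inevaluable, replaced |

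The conflict needs no assumption. Its size does.

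**Step 1. The plan's own figures (9.5.1).** X is binomial with n = 10 and true rate p.
- Serious, p = 0.30: P(X ≥ 1) = 1 − 0.70^10 = 0.972 (stated 97%).
- Serious, p = 0.01: P(X = 0) = 0.99^10 = 0.904 (stated 90%).
- Concerning, p = 0.30: P(X ≤ 5) = 0.953 (stated 95%).
- Concerning, p = 0.70: P(X ≥ 6) = 0.850 (stated 85%).

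All four reproduce.

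**Step 2. Effect of a literal 7.1.4.** Take p over the full dosing window, and let f be the share of DLT patients whose DLT falls before SRS. They are removed and replaced, so the rate among evaluable patients is

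q = p(1 − f) / (1 − pf).

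**Step 3. An illustrative f.** The documents give no DLT timing. Assume DLTs spread evenly over dosing. The lead-in is 5 to 9 days (4.1.4), and the one-month MRI falls between day 25 and day 40 (Appendix VIII: day 30, −5 to +10).
- Low: f = 5/(5 + 40) = 0.111.
- High: f = 9/(9 + 25) = 0.265.

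**Step 4. Results.**

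| Case | f = 0 | f = 0.111 | f = 0.265 |
|---|---|---|---|
| Concerning, p = 0.70: q | 0.700 | 0.675 | 0.632 |
| P(X ≥ 6), flagged | 0.850 | 0.803 | 0.710 |
| Serious, p = 0.30: q | 0.300 | 0.276 | 0.240 |
| P(X ≥ 1), flagged | 0.972 | 0.960 | 0.935 |

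Example: q = 0.70 × 0.889 / (1 − 0.70 × 0.111) = 0.622 / 0.922 = 0.675.

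The chances of passing a tolerable dose only rise: from 90% to 91-93% at a 1% serious rate, and from 95% to 97-98% at a 30% concerning rate. If 7.1.2 governs, f = 0 and the first column applies.

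**The case against.** The best defence is that 7.1.2 sets the trigger and 7.1.4 decides only who fills the ten slots. Section 7.1.4 also fits a pattern: 4.1.9.2, 6.1 and 8.2.1 treat other patients who fail before SRS as inevaluable. This reading is workable and costs nothing in detection. But no section states it, 5.3.1 writes both thresholds on evaluable patients, and 7.1.4 follows 7.1.2 and names both toxicity types. Reading 7.1.4 instead as a specific exception leaves it in conflict with 2.3.1 and 9.1.1.

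Oversight is a fair point as well. The data safety committee reviews all data before the randomized portion (5.2), serious adverse events are reported within 24 hours (7.3.1), and patients withdrawn after starting treatment are followed for adverse events for 30 days (7.3.3). A reader might infer that early DLTs would go unseen; the documents do not support that. These provisions make the events visible but do not settle whether they count.

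Three further inferences go too far:
- *That the figures in 9.5.1 prove every DLT from the first dose was meant to count.* Section 9.5.1 does not say over which window, or in which patients, its true rates are defined. If they are rates among evaluable patients, the same four figures follow under 7.1.4.
- *That the glucose-monitoring choice in 5.4.2.2 is distorted.* Its count is not written on evaluable patients.
- *That 7.2.3, the same sentence for the randomized portion, biases the toxicity comparison.* The restriction to evaluable patients in 9.4 is stated for endpoints other than CTCAE-graded toxicities, and no stopping rule in that portion uses DLT counts.

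**Conclusion.** The contradiction stands on the text alone and should be fixed, because it sits in the pilot's primary endpoint and its dose decision. Followed literally, 7.1.4 removes DLTs from the first 5 or more days of dosing and biases the rule toward passing the dose; if 7.1.2 governs, the loss is zero.

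The size is only an illustration. With rates defined over the full dosing window and an even spread of DLTs (11-26% before SRS), detection falls by about 5 to 14 points for a 70% concerning rate and by about 1 to 4 points for a 30% serious rate. Earlier clustering would make the loss larger and later onset smaller. Section 5.1 allows a lead-in longer than 5 days without a stated cap, so these are not bounds. Confidence is high in the contradiction and low in any particular size.

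**What to change.** Limit 7.1.4 to evaluability for the MRI and efficacy endpoints. State that any pilot patient who takes at least one dose and has a concerning or serious toxicity, before or after SRS, is evaluable for the DLT endpoint and counts in the 1-of-10 and 6-of-10 rules. Replace for that endpoint only patients who leave before the one-month visit without a DLT. In the same edit, align 7.2.3 with 5.3.2 for consistency.

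The cost is a paragraph and one matching line, with no added patients or procedures. The downside is that a dose reduction or termination becomes slightly more likely than under a literal 7.1.4.

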7.2 Randomized Portion

7.2.1 Non-Micronized glyburide (1.25 mg po BID) or placebo (1 tablet po BID) should be administered orally twice a day beginning at least 5 days prior to SRS. The investigational medication will be taken in the morning with breakfast and in the evening with dinner. All patients and the study team will be blinded to the investigational medication which will continue until the evening dose on the day of the one month post SRS follow-up MRI. If the patient misses a dose at any time, it will not be made up. All doses (whether missed or taken) should be recorded in the medication administration log.

7.2.1.1 In the event of a DLT in the Pilot Portion requiring a dose reduction and this dose is considered safe, patients will receive either a reduced dose of non-micronized glyburide (now at 0.75 mg po BID) or the placebo (1 tablet po BID). The investigational medication will be taken in the morning with breakfast and in the evening with dinner. All patients and the study team will be blinded to the investigational medication which will continue until the evening dose on the day of the one month post SRS follow-up MRI. If the patient misses a dose at any time, it will not be made up. All doses (whether missed or taken) should be recorded in the medication administration log.

7.2.2 In the event of a DLT in the Randomized Portion of the study, the patient who experienced the DLT will stop their investigational medication immediately. Other patients currently on study at the time of the DLT will continue on study treatment without interruption.

7.2.3 If a patient suffers a DLT (either a “*concerning toxicity*” or a “*serious toxicity*”) after registration but before SRS, he/she will be removed from the protocol and considered inevaluable.

7.3 Data Safety Monitoring and Adverse Events

7.3.1 Data and Safety Monitoring / Quality Assurance Committee

This study will follow the UAB Data and Safety Monitoring Plan maintained by the UAB Comprehensive Cancer Center. This includes monthly reporting to the Clinical Trial Monitoring Committee for all adverse events. Serious adverse events are also reported to the UAB IRB and the study PI within 24 hours.

